**Double-Blinded Randomized Prospective Trial of Intranasal Capsaicin Treatment for Non-
Allergic Irritant Rhinitis**

NCT02493257

Version Date: 11/18/2019

IRB NUMBER: HSC-MS-14-0173
IRB APPROVAL DATE: 11/18/2019

Protocol Title: Double-Blinded Randomized Prospective Trial of Intranasal Capsaicin Treatment for Non-Allergic Irritant Rhinitis

Principal Investigator: [name]

Co-Investigators: [name] PhD; [name]; [name]

Study Coordinator: [name] PhD

Population: The study population will consist of patients with non-allergic irritant rhinitis (NAIR) as defined by history (symptoms of nasal congestion, rhinorrhea, nasal itching or sneezing upon exposure to nasal irritants) and positive optical rhinometer (Rhinolux™, Rhios GmbH, and Germany) response with intranasal challenge with capsaicin. Participants will be sought from those presenting to the outpatient Otolaryngology clinic at the University of Texas Medical School at Houston. Patients included in the study will be between the ages of 18 and 70 with no history of sinonal surgery, intranasal steroid use for more than 4 weeks, intranasal or systemic antihistamine for 3 days, intranasal or systemic decongestants for 3 days, chronic rhinosinusitis, inflammatory or granulomatous diseases, asthma, allergic rhinitis, immunocompromised state or radiation to the head and neck.

Sample size: 11 participants will need to be recruited to each group (experimental and control) to detect a significant post-treatment change. In order to reach our target enrollment of 22 participants we expect to screen 60 subjects.

Number of sites: single site

Study duration: 13 weeks

Subject duration: 13 weeks

General Information: The proposed study seeks to investigate the effect of intranasal capsaicin treatment in patient with Non-allergic irritant rhinitis (NAIR), as well as evaluate optical rhinometry (ORM) as a means to quantify symptomatic improvement in NAIR patients during and after treatment.

Background Information:

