The study will consist of patients with non-allergic irritant rhinitis (NAIR) as defined by history (symptoms of nasal congestion, rhinorrhea, nasal itching or sneezing upon exposure to nasal irritants) and positive optical rhinometer (Rhinolux™, Rhios GmbH, and Germany) response with intranasal challenge with capsaicin (17). Participants will be sought from volunteers and those presenting to the outpatient Otolaryngology clinic at the University of Texas Medical School at Houston. Patients included in the study will be between the ages of 18 and 70 with no history of sinonasal surgery, intranasal steroid use for more than 4 weeks, intranasal or systemic antihistamine for 3 days, intranasal or systemic decongestants for 3 days, chronic rhinosinusitis, inflammatory or granulomatous diseases, asthma, allergic rhinitis, immunocompromised state or radiation to the head and neck.

Allergy Testing to Identify and Exclude Subjects with Allergic Rhinitis

All previously consented subjects with history consistent with NAIR will be screened with a skin prick test (Multi-Test II Lincoln Diagnostics, Decatur, IL USA) to 6 common allergens including dust mite, mixed mold extract, cat hair, grass pollen, insect extracts, and bermuda grass extract to exclude allergic rhinitis. Those with confirmed negative skin prick testing will be eligible for the study.

Capsaicin Challenge and Optical Rhinometry

The optical rhinometer apparatus is applied to either side of the nasal dorsum according to the manufacturer's instructions. A one-minute baseline recording will be obtained and averaged. Capsaicin solution (Sigma Chemical, St. Louis, MO USA) will be diluted in 1% ethanol vv and 0.9% normal saline. 1% ethanol in 0.9% normal saline will serve as the vehicle solution. A mucosal atomizer device (MAdomizer, Wolfe Tory Medical, Inc Salt Lake City, UT USA delivering a 100 μ l solution will be used to deliver a dose of capsaicin totaling 1.5 μ g of capsaicin (0.05 mM) to the anterior face of the inferior turbinate of each nare. The maximum change in optical density (OD) will be recorded. Patients with a maximum change in OD of at least 0.2 will be considered a positive response and included in the study.

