5 consecutive applications of capsaicin or placebo will be administered intranasally, with 1 hour between each application. Fifteen minutes prior to each application of medication, the nasal mucosa will be anesthetized with 100 ul of 1% lidocaine will be applied to each nasal cavity via MAD for all study participants. The lidocaine should not alter the nasal mucosa reaction to capsaicin; and is meant to anesthetize the area from the mild stinging of capsaicin. In fact, because lidocaine has a very mild stinging sensation at times; it can serve to mask the stinging one may get with intranasal capsaicin. Using the MAD, 100 μ L of 1% ethanol in 0.9% saline solution (Group A) or 0.8 mL solution with (0.1mmol/l) of capsaicin in 1% ethanol in 0.9% saline (Group B) will be delivered to each nasal cavity. On this day, they will not need to undergo optical rhinometry. Patients will fill out composite symptoms scores before and five minutes after 1st and 5th treatments. Patients who complete this portion of the experiment will receive \$50 dollars in compensation as well as parking.

Patients will then follow up 4 and 12 weeks after initiating treatment. At the 4 week and 12 week follow-up appointments, subjects will undergo capsaicin challenge followed by ORM and composite symptom score of nasal symptoms will be reported. Patients who complete both follow up visits will receive \$25 dollars in compensation as well as parking.

Study Protocol

Compensation:

In summary, patients that undergo the screening process and complete the skin prick testing and intranasal capsaicin challenge and ORM will be compensated \$25 as well as parking validation. Patients that undergo the treatment will be compensated \$50 plus parking for completing that day. Patients that complete the study and return 4 and 12 weeks post treatment, will be compensated \$25 plus parking.

Data and Safety Monitoring:

Previous studies have shown that the concentration of capsaicin that will be used is generally well tolerated.

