Regarding the lidocaine, it is administered routinely in our clinic prior to nasal endoscopy and flexible laryngoscopy exams. Side effects can include minor stinging and burning when applied to the nose. Because it is an intranasal spray, there is a risk that patients will swallow it and may have difficulty swallowing for up to 45 minutes after application. We express to patients that they should avoid eating or drinking anything up to 45 minutes after the lidocaine application.

Regarding skin prick testing, patients may have mild discomfort where the skin is pricked. They may have symptoms such as itching, a stuffy nose, red watery eyes, or a skin rash. Rarely, people can have anaphylaxis, but this usually only occurs with intradermal testing, which we will not be performing. If patients become short of breath, we do have oxygen available in the clinic.

Patients will be educated to call the outpatient Otolaryngology clinic at the University of Texas Medical School at Houston if there are any adverse effects.

Human Subjects:

Participants will be sought from those presenting to the outpatient Otolaryngology clinic at the University of Texas Medical School at Houston. Patients included in the study will be between the ages of 18 and 70 with no history of sinonasal surgery, intranasal steroid use for more than 4 weeks, intranasal or systemic antihistamine for 3 days, intranasal or systemic decongestants for 3 days, chronic rhinosinusitis, inflammatory or granulomatous diseases, asthma, allergic rhinitis, immunocompromised state or radiation to the head and neck.

This is a small study of only 22 subjects total and as addressed previously we anticipate screening 60 subjects in order to complete our enrollment. . Our practice consists of adult patients with a majority of who speak and read English. Therefore, it is unlikely to exclude a subject from the study because they do not speak or read English

Statistical Analysis:

Justification of sample size:

Using [name] paper (17) : his article showed the average maximum optical density in NAIR patients was 0.2 (SD 0.051), seen when using the 0.05 mM concentration of capsaicin during the capsaicin challenge and ORM. Healthy control subjects had a mean maximal OD change of 0.174 (SD 0.034). This was significant to $p=0.01$. Based on this data, 11 patients will need to be recruited to detect a significant post-treatment change.

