Student's t-test will be used to compare the mean change in composite symptom scores pre and post-treatment in both groups. Student's t-test will also be used to compare changes in maximal optical density in response to capsaicin challenge pre- and post-treatment in both

groups. Statistical significance will result if $p < 0.05$. The Spearman Rank Correlation will be used to analyze associations between composite symptom scores and changes in OD.

Ethics:

IRB approval will be sought from CPHS

Data Handling and Record Keeping: In order to maintain confidentiality, a data sheet with patient's names and data collected for the study (see data sheet) will be stored in a locked file cabinet within the department of Otorhinolaryngology. Access to data sheets in patient will be limited to co-investigators and research coordinator. Only de-identified data or collective data will be shared.

Quality control and assurance: In order to confirm that the diagnosis of non-allergic irritant rhinitis is accurate and made in an unbiased manner, a history of rhinitic symptoms will be confirmed with objective skin testing.

All datasheets will be recorded by PI and reviewed by at least one of the other 3 co-investigators to ensure accuracy in the recording of clinical data.

Publication Plan: This study has been funded by the American Association of Otolaryngic Allergy (AAOA) Foundation Grant. Results from this study will be presented at a future AAOA national meeting and initial publication rights will be given to the International Forum of Allergy and Rhinology.

All enrolled subjects will be notified of any publication resulting from this study, but these publications will present data on only the aggregate group.

REFERENCES

2. Hummel T. Assessment of intranasal trigeminal function. *Int J Psychophysiol*. 2000 May;36(2):147-55.

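### Unadjusted t-tests on change fix the baseline slope at 1. With 11 per arm this over-corrects chance imbalance and loses precision, materially for symptoms and only slightly for OD.

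*Combined protocol and SAP*

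**What the plan says.** The Statistical Analysis section gives one test for each outcome. For symptoms: "Student's t-test will be used to compare the mean change in composite symptom scores pre and post-treatment in both groups". For OD: "Student's t-test will also be used to compare changes in maximal optical density in response to capsaicin challenge pre- and post-treatment in both" groups. The threshold is p below 0.05. No covariate or adjusted model is named, and no stratified randomisation is described.

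The baselines exist. OD is measured at visit 1, and it also decides entry: "Patients with a maximum change in OD of at least 0.2 will be considered a positive response and included in the study" (Capsaicin Challenge and Optical Rhinometry). Under Study Procedure, a composite symptom score is recorded at visit 1 before the challenge, and further scores are taken on the treatment day: "Patients will fill out composite symptoms scores before and five minutes after 1st and 5th treatments". Follow-up is at 4 and 12 weeks. The Sample size item at the front of the protocol gives the arm size: "11 participants will need to be recruited to each group (experimental and control) to detect a significant post-treatment change".

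**The concern.** Subtracting the baseline from the follow-up value assumes that a patient who starts one unit higher would, untreated, finish one unit higher. If the spreads before and after are similar, the expected carry-over is only r units. The change score then removes too much. The arm that happens to start higher shows a larger fall for reasons unrelated to treatment, and the estimate is noisier than it need be.

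With 11 patients per arm, chance imbalance is common and there is little precision to spare. ANCOVA estimates the slope from the data and uses only measurements that the trial already takes.

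**Working it through.** **The plan's own figure.** The section Justification of sample size cites OD of 0.2 (SD 0.051) in NAIR patients and 0.174 (SD 0.034) in healthy controls. The difference is 0.026 and the pooled SD is √[(0.051² + 0.034²)/2] = 0.0433. A two-sided, two-group comparison with 80% power needs 2 × (1.96 + 0.84)² × (0.0433/0.026)², about 44 per arm. The stated 11 is therefore not reproduced as a two-group size. That is a separate matter, and 11 per arm is taken as given below.

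**Assumptions.** r is not in the documents; 0.3 to 0.9 is shown. Values are taken as normal, with equal spread before and after in unselected patients. For OD, the cited NAIR distribution is cut at 0.2.

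**Chance imbalance.** The between-arm baseline difference has SD √(2/11) = 0.426 baseline SDs. P(imbalance above 0.5 SD) = 2[1 − Φ(0.5/0.426)] = 0.241.

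**Effect of an imbalance.** A change score shifts by −(1 − r) times the imbalance. For 0.5 SD in symptoms this is 0.35, 0.25 or 0.15 SD at r = 0.3, 0.5, 0.7. For OD, the enrolled baseline has mean 0.2 + 0.051√(2/π) = 0.241 and SD 0.051√(1 − 2/π) = 0.0307. The shift is (1 − r) × 0.5 × 0.0307 = 0.011, 0.008 or 0.005. That is 41%, 30% or 18% of the 0.026 gap, or about 21%, 15% or 9% of an assumed effect of 0.05.

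**Variance, symptoms (no entry cut).** Change score: 2(1 − r)s². ANCOVA: (1 − r²)s², times 1 + 1/(2n − 4) = 1 + 1/18 = 1.056 for estimating the slope. The ratio is 1.056(1 + r)/2.

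**Variance, OD (baseline cut at its mean).** Change score: s²[(1 − r²) + (1 − r)²(1 − 2/π)]. ANCOVA: s²(1 − r²), times 1.056. At r = 0.5: 0.75/(0.75 + 0.25 × 0.363) = 0.892, and 0.892 × 1.056 = 0.942.

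| r | Symptoms, ANCOVA/change | OD before slope cost | OD after slope cost |
|---|---|---|---|
| 0.3 | 0.686 (31% lower) | 0.836 | 0.883 (12% lower) |
| 0.5 | 0.792 (21% lower) | 0.892 | 0.942 (6% lower) |
| 0.7 | 0.897 (10% lower) | 0.940 | 0.992 (1% lower) |
| 0.8 | 0.950 (5% lower) | 0.961 | 1.015 (1.5% higher) |
| 0.9 | 1.003 (no gain) | 0.981 | 1.036 (3.6% higher) |

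Simulation of the same model agrees to about a percentage point (OD reductions of roughly 11%, 5 to 6% and 1% at r = 0.3, 0.5, 0.7).

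**What this means for symptoms.** To match ANCOVA with 11 per arm, a change-score analysis would need 11/0.686 = 16.0, 11/0.792 = 13.9 or 11/0.897 = 12.3 per arm. Simulated power for an assumed 1-SD effect rises from 47 to 62%, 61 to 70% and 82 to 86%.

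**What this means for OD.** Simulated power for an assumed effect of 0.05 rises from 56 to 61%, 66 to 69% and 84 to 85%.

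**Dependence on imbalance.** At r = 0.3, 0.5, 0.7 the simulated correlation between the change-score estimate and the baseline imbalance is about −0.59, −0.50, −0.38 for symptoms and −0.41, −0.32, −0.24 for OD. For ANCOVA it is about 0. Type I error of the between-arm test in the OD simulation is about 5% for both methods.

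**The case against.** The best defence is that the planned test is valid. Randomisation makes the between-arm change-score comparison unbiased on average and its error rate holds, so the choice is one of efficiency. The size of the gain rests on an r that the documents do not give. For OD, the only outcome used in the sample-size paragraph, the gain is small and reverses at high r. All of this stands, and it limits the point.

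Four stronger readings are tempting, and the documents do not support them:

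- *Baseline is ignored and imbalance goes uncorrected.* A change score does use baseline, with a fixed slope of 1. The fault is over-correction.
- *Selecting patients on OD makes the loss worse, or forces the slope below 1.* Cutting on baseline leaves the slope of follow-up on baseline unchanged. A slope below 1 comes from imperfect correlation with similar spreads. The cut narrows the baseline and so shrinks the gain from ANCOVA.
- *The criticism holds whatever is being tested.* The wording about pre and post in both groups could mean a separate paired test within each arm, and the sample-size text fits that too: "Based on this data, 11 patients will need to be recruited to detect a significant post-treatment change". On that reading there is no between-arm estimate for imbalance to disturb. Regression to the mean, which cancels between arms, would enter instead: after the cut, mean OD in the vehicle arm would move by −(1 − r) × 0.0407, or −0.028, −0.020, −0.012 at r = 0.3, 0.5, 0.7. The undefined contrast therefore has to be settled first.
- *ANCOVA would make 11 per arm enough.* At the plan's own standardised effect (0.026/0.0433 = 0.60), ignoring the entry cut, power moves only from 20 to 28%, 27 to 32% and 41 to 45%.

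**Conclusion.** The point holds as a matter of efficiency and of sensitivity to chance imbalance, provided the intended comparison is between arms. For symptoms the gain is worth having at r up to about 0.7 (variance 31%, 21%, 10% lower at r = 0.3, 0.5, 0.7) and is gone by r = 0.9. For OD it is modest (about 11 to 12%, 5 to 6%, 1%), with a loss of about 2 to 4% at r = 0.8 to 0.9. In both outcomes ANCOVA removes the dependence of the estimate on an imbalance that exceeds 0.5 SD in about one trial in four. A reader might infer that the planned between-arm result would be biased or invalid. It would not be, on average over randomisations.

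The sizes rest on the assumed r, on normality with similar spreads before and after, and, for OD, on screened patients resembling the cited NAIR sample.

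**What to change.** In the Statistical Analysis section:

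1. State that the comparison is capsaicin versus vehicle at one named follow-up visit (4 or 12 weeks).
2. Replace both t-tests with ANCOVA of the follow-up value, with arm as factor and the matching baseline as covariate: visit 1 OD for OD, and the visit 1 composite score for symptoms.
3. Report the adjusted capsaicin-minus-vehicle difference with its 95% CI.

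Averaging the visit 2 pre-treatment score into the symptom baseline is optional. Study Procedure places lidocaine fifteen minutes before each application and says only that the score comes before the 1st treatment, so if that score is used, its timing relative to lidocaine must be stated.

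The cost is SAP wording and one degree of freedom, with no new data if the visit 1 scores are used. The sample-size justification needs its own revision.

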A composite symptom score will be recorded based a commonly used rhinitis rating system as recommended by the FDA for clinical trial studies on allergic rhinitis (<http://www.fda.gov/downloads/Drugs/GuidanceComplianceRegulatoryInformation/Guidances/ucm071293.pdf>). Each of the following 4 symptoms: nasal itching/tingling, nasal congestion, sneezing and rhinorrhea, will be rated on a 0-3 scale of severity (Appendix B) and a summed composite score will be recorded for each subject.

Capsaicin Treatment Concentration

The capsaicin solution will be prepared by using the formula previously reported by Van Rijswijk et al; (0.1mmol/l) diluted in ethanol and 0.9% normal saline (19). Using the MAD, 0.8mL will be delivered to each nasal cavity for a total of 24.4 ug per nasal cavity.

Study Procedure:

[figure not shown]
There will be a total of 4 visits. On the first visit, patients will be consented and undergo skin prick testing, the capsaicin challenge and Optical Rhinometry. Prior to undergoing the capsaicin challenge, a composite symptom score will be recorded. Patients with confirmed negative skin prick testing, and positive response on ORM will be eligible for the study and will be asked to return for treatment. Those who are not eligible will not be responsible for any costs associated with screening and will be compensated for parking as well as \$25.00 for their time.

At the second visit, the NAIR patients will have been randomized and blinded into two groups: Group A will be treated with vehicle spray; and Group B will be treated with the capsaicin spray. The PI will be blinded to the treatment. A member of the research team, which consists of Drs. [name], [name], [name], and [name] (research coordinator), will assist during the randomization and distribution of appropriate pre-made medications so that the PI and subjects remain blinded.

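### The t-tests of pre- to post-treatment change leave the two follow-up visits undefined and unadjusted for baseline; one baseline-adjusted repeated-measures model with a named contrast would serve better, with a gain that depends on unstated correlations

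*Combined protocol and SAP*

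**What the plan says.** Baseline: under Study Procedure, the first visit includes the capsaicin challenge with optical rhinometry (ORM), and "Prior to undergoing the capsaicin challenge, a composite symptom score will be recorded". The symptom score is also taken on the treatment day, around the first and fifth applications.

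Follow-up: the same section states that "At the 4 week and 12 week follow-up appointments, subjects will undergo capsaicin challenge followed by ORM and composite symptom score" is reported. Each patient therefore has two planned follow-up readings per outcome.

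Analysis: the Statistical Analysis section says "Student's t-test will be used to compare the mean change in composite symptom scores pre and post-treatment in both groups", and for optical density (OD) that "Student's t-test will also be used to compare changes in maximal optical density in response to capsaicin challenge pre- and post-treatment" in both groups. It adds a 0.05 significance threshold and a Spearman correlation. It names no follow-up visit, no way of combining visits, no baseline adjustment and no rule for missed visits.

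Size: the Sample size paragraph says "11 participants will need to be recruited to each group (experimental and control) to detect a significant post-treatment change". Target enrollment is 22, so there is no allowance for dropout.

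**The concern.** A Student's t-test takes one value per patient, and the schedule supplies two follow-up values. The analyst must test each visit separately, pick one, or reduce the two to a summary. The plan fixes none of these, so the choice stays open until the data are seen.

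If the tests are run visit by visit, each uses one follow-up reading and excludes a patient absent that day even if the other visit was attended. One missing patient is 1/11 = 9% of an arm. Incomplete follow-up is foreseeable: the follow-up payment depends on completing both visits.

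With so few patients, precision matters. The baseline reading and the second follow-up are already being collected, and the planned test may make poor use of them.

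**Working it through.** **The plan's own figure.** The documents give no within-patient correlation and no variance for a change, so no efficiency figure can be reproduced. The one figure available is 11 per group. Justification of sample size gives means of 0.2 (SD 0.051) and 0.174 (SD 0.034).
- Difference: 0.2 − 0.174 = 0.026. Pooled SD: √[(0.051² + 0.034²)/2] = 0.0433.
- Two groups, two-sided 0.05, 80% power (sidedness and power are assumptions): n = 2 × (1.960 + 0.842)² × 0.0433² / 0.026² = 43.6, so 44 per group. With 11 per group, power is about 29%.
- A one-sided, one-sample calculation with the healthy-control SD does give 11: (0.034 × (1.645 + 0.842) / 0.026)² = 10.6. That is not a comparison of two arms.

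**Assumptions for the efficiency check.** The contrast is between arms. The SD σ is the same at all three times, and one correlation r holds among baseline, week 4 and week 12. The variances are large-sample ones, ignoring the small cost of estimating a baseline slope in 22 patients. Entries are per-patient variances in units of σ²; the factor 2/n for the arm difference cancels in every ratio.

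| Analysis | Formula | r = 0.3 | r = 0.5 | r = 0.7 |
|---|---|---|---|---|
| A. Change, one visit | 2(1 − r) | 1.40 | 1.00 | 0.60 |
| B. Mean of two changes | 1.5(1 − r) | 1.05 | 0.75 | 0.45 |
| C. Baseline-adjusted, one visit | 1 − r² | 0.91 | 0.75 | 0.51 |
| D. Baseline-adjusted, average of two visits | (1 + r)/2 − r² | 0.56 | 0.50 | 0.36 |

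Savings at r = 0.3, 0.5 and 0.7:
- B against A (averaging only): 25% at every r.
- C against A (baseline adjustment only): 35%, 25%, 15%.
- D against A (both): 60%, 50%, 40%.
- D against C (second visit, given baseline adjustment): 38%, 33%, 29%.

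**Unequal correlations.** Let b be the correlation of baseline with each follow-up and f the correlation between follow-ups. D/C becomes [(1 + f)/2 − b²] / (1 − b²). Over b = 0.2 to 0.5 and f = 0.3 to 0.9 the saving runs from 5% (b = 0.2, f = 0.9) to 47% (b = 0.5, f = 0.3). The Capsaicin Challenge and Optical Rhinometry section admits only patients with an OD change of at least 0.2. This truncates baseline OD and tends to make b smaller than f, which favours the lower part of the range. For example, b = 0.2 and f = 0.7 give (0.85 − 0.04)/0.96 = 0.84, a 16% saving.

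**One deciding visit.** With complete data, the other visit adds about 0%. If a fraction m of patients miss week 12 but were seen at week 4, the week-4 reading saves about m × r². For m = 0.1 this is 0.9%, 2.5%, 4.9%; for m = 0.2 it is 1.8%, 5.0%, 9.8%. These figures are before baseline adjustment. After it, r is replaced by the partial correlation r/(1 + r) = 0.23, 0.33, 0.41, and at m = 0.2 the saving falls to 1.1%, 2.2%, 3.4%.

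**Effect on power.** Suppose the SD of a one-visit change is 0.0433 (assumption). A 25% variance cut then needs 33 per group and gives 37% power at 11; a 50% cut needs 22 and gives 51%. A 60% cut needs 43.6 × 0.4 = 17.4, so 18 per group, still above 11.

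**The case against.** The strongest reply is that the plan is silent rather than wrong. A reader might infer that it tests one visit at a time and discards anyone who misses that visit. The text says neither. A t-test on each patient's mean change over weeks 4 and 12 fits the wording, uses both readings and could keep a patient seen once. This objection stands, so the loss of data follows from one reading of the plan and is not its stated rule. What remains is that the choice is not fixed in advance and that no version of the t-test adjusts for baseline.

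A reader might also infer that a repeated-measures model cuts the variance by about a third. That figure compares two baseline-adjusted analyses, neither of which is in the plan. It requires an equal correlation near 0.5 and applies only to the average of weeks 4 and 12. Nor is the 50% saving over a one-visit change score at r = 0.5 due to the second visit alone: baseline adjustment by itself brings the variance from 1.00 to 0.75.

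The wording on changes in both groups could also mean paired tests within each arm; the ratios above do not describe that reading. Finally, the model is not a cure for missing data. It relies on a weaker assumption than analysing attenders only, but it is biased too if attendance depends on outcomes that were not observed, and it omits patients with no follow-up. The documents give no dropout rate.

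**Conclusion.** The concern holds in limited form. The plan has a baseline and two follow-up readings per outcome, but specifies only t-tests of change, without a named visit, a rule for combining visits, baseline adjustment or handling of a missed visit. A baseline-adjusted repeated-measures model is a better choice for the between-arm comparison.

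The size of the gain rests on assumed correlations. It is 40% to 60% against a one-visit change-score test for the averaged effect, under equal correlations of 0.3 to 0.7. The second visit's own share, given baseline adjustment, is anywhere from about 5% to 47% if correlations are unequal, which is plausible for OD. If one visit decides, the gain comes mainly from baseline adjustment.

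A reader might infer that better use of the data makes 11 per group adequate. On the plan's own figures it does not. This is an improvement worth making, not a flaw that invalidates a t-test on complete data.

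**What to change.** In the Statistical Analysis section, for each outcome:
- Fit one repeated-measures model to all randomised patients with any follow-up: arm, visit, arm-by-visit and baseline, with unstructured covariance over the two visits and small-sample degrees of freedom (for example Kenward-Roger).
- State which reading is the baseline; for the symptom score there is more than one pre-treatment candidate.
- Name in advance the deciding between-arm contrast: one visit, or the average of weeks 4 and 12. If one visit decides, take its estimate from this model, so that a patient seen only at the other visit still contributes.
- Report the arm difference at each visit with 95% confidence intervals.
- State how missed visits are handled and the assumption this makes.

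The cost is SAP wording and a standard model, with no added patients, visits or procedures. The main downside is that an averaged effect is diluted if the effect builds or fades between weeks 4 and 12; the by-visit estimates would show this. The sample size justification needs separate attention.
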